**Specific Aim 2:** Evaluate whether increases in cardiovascular fitness mediate cognitive improvement. Cardiovascular fitness will be estimated with a reliable and valid measure of oxygen uptake (VO2max) prior to and after 12 weeks of the AE vs. CONT intervention and at 8 weeks *post-training follow up*. Estimated VO2max is the most appropriate test as it accounts for initial fitness level of the participant without the physically exhausting and frightening experience of a full VO2max test. We predict that estimated VO2max improvement in the AE group will predict cognitive gain with training at 12 weeks and 8 weeks *post-training follow up*.

**Specific Aim 3:** Compare changes in measures of everyday functional abilities (U. California San Diego Performance-Based Skills Assessment, UPSA) in the AE vs. CONT training groups. We predict that the AE group will show greater gains in the UPSA than CONTs at 12 weeks and 8 weeks *post-training follow up*.

Improvements in cognitive function and skills of everyday living in SCZ are highly resistant to treatment with our current choices of medications. SCZ is generally a life-long condition: thus the disabilities with which these patients struggle will require treatment from the VA for the life of the patients. If AE leads to enhanced cognitive

functioning of these patients in everyday activities, AE could become a valuable treatment modality for the rehabilitation of SCZ patients, having dual benefits on both cognition and physical health. Hence this proposal is highly relevant to the VA mission of reducing impairments and rehabilitating our patients.

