#### **(2) Secondary outcome measures:**

**a.** To confirm the cardiovascular effects in the AE group we will perform an exercise test on all participants. Cardiovascular fitness will be estimated by the YMCA sub-maximal cycling protocol at Baseline, *Endpoint (12 weeks), and at 8 weeks post-training follow up*. Estimated **VO2max** is the most appropriate test as it accounts for initial fitness level of the participant without the physically exhausting and frightening experience of a full V0max test. This is particularly critical since our population will be sedentary. This test uses an "extrapolation" method in which heart rate (HR) workload values are obtained at 4 points and extrapolated to predict workload at the estimated maximum HR (MHR) (e.g. 220 minus age in years). VO2max is then calculated from the predicted maximum workload. Participants will be asked to ride a stationary bicycle for 4 three-minute stages. The first stage is a warm-up at 50 revolutions per minute (RPM) at a power level of 25 watts. During all testing stages, HR will be continuously monitored and will not exceed 85% of age-predicted maximum HR. Average HR during the final 30 seconds of the 2nd and 3rd minutes will be plotted against workload. Three-minute trial workloads will be chosen based on the participants' HR at the end of the warm-up period. The fourth 3-minute stage will be a cool down period at the end of the test. Participants will be allowed to stop the test at anytime if they feel faint, dizzy, short of breath, or for any other reason.

**b.** Ultimately, the goal of AE for cognitive remediation is to help our patients achieve improvements in real-world functioning and psychiatric stability. The U. California San Diego Performance-Based skills assessment (**UPSA**) is a measure of functional ability that can detect immediate improvements in the ability to carry out functionally meaningful tasks (Patterson et al. 2001; Harvey et al. 2007). It has excellent test-retest reliability (Leifker et al. 2010) and is able to quantify the potential for functional improvement with cognitive change (Green et al. 2011). As such, the UPSA is an excellent predictor of real-world functional outcomes (Mausbach et al. 2008; see Leifker et al. 2011 for a review). This literature supports our plan to use this measure in **SA3** at Baseline, *Endpoint (20 weeks), and 8 weeks post-training follow up*.

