**Statistical analysis plan**  
**Specific Aim 1:**  
 Compare the feasibility and effectiveness of AE

training to a CONT condition at the end of treatment (12 weeks) in VA participants with SCZ or schizoaffective disorder. We predict that the completion of this training will be feasible in our VA population, and that the AE group will exhibit significantly greater improvement on the MCCB than the CONT group.

**Statistical analysis:** Basic statistical comparisons will be performed preliminarily before using a unified statistical approach. Two-sample t-tests using the change in cognitive tests and functional scales as dependent variables will compare AE to CONT participants. The statistical methodology includes both initial descriptive comparisons followed by a more complex unified statistical approach. Spec Aim 1 will ultimately be addressed in a full Merit project using a linear mixed model that is conceptually similar to analysis of variance (ANOVA). However, in this Pilot proposal we will build intuition about the model and the expected results by performing simple comparisons of direct interest prior to complex modeling. To accomplish this preliminary descriptive step and test our hypothesis we will use a univariate analysis of covariance (ANCOVA) looking at change scores with baseline measures plus age, sex, and anticholinergic load as covariates. We predict that greater anticholinergic load of medication will predict poorer improvement. With a sample size of 20 completers per treatment group, we will be sensitive to a within-between interaction effect size of  $f=0.456$  at an alpha level of 0.05 with a power of 0.80. This can be interpreted as a sensitivity to between group difference in change scores of 9.5 MCCB composite t-score units (mean=50, SD=10), which is a meaningful clinical effect.

We will also undertake exploratory (non-inferential) analyses to estimate the strength of association of multiple dependent measures from the cognitive and functional domains. Data reduction via factor analysis will be performed for the MCCB battery data to reduce the number of dependent measures. Because the analysis of this data will employ multiple independent analyses, uncorrected significance tests will not be appropriate for inferential interpretation. However, uncorrected p-values will be reported as arbitrary criteria of effect size strength in deference to widespread use in social science for exploratory analyses.

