To assess feasibility we will collect data on the numbers of SCZ participants who are potentially interested in participation, the number who screen out and for what reasons, the number of drop outs, and the reasons for their dropping out. We will also collect data on attendance and barriers to attendance. For these measures we will compute descriptive statistics. These data will inform proposals for fully powered future studies.

**Specific Aim 2:** Evaluate whether increases in cardiovascular fitness ( $VO_2\text{max}$ ) mediates cognitive improvement. We predict that the degree of estimated  $VO_2\text{max}$  improvement in the AE group will predict the degree of cognitive improvement with training.

**Statistical analysis:** We will assess potential mediator effects of  $VO_2\text{max}$  as well as potential moderator effects of age, sex, and anticholinergic load to better formulate covariates in future models. The association between potential moderators and cognitive improvement will be evaluated through use of bivariate and multiple correlations; only significant associations will be further assessed as possible moderators. The assessment of  $VO_2\text{max}$  as a potential mediator will be evaluated using partial correlation coefficients from the regression model. With a total sample size of 20 participants in the treatment group, we will be sensitive to a bivariate effect size of  $r = 0.428$  at an alpha level of 0.05 with a power of 0.80. This would allow us to detect differences of up to 18% in potential moderator variables. In a multiple regression with four predictor variables (because of issues of multicollinearity with anticipated high degrees of correlation possible between the potential moderator variables, it is doubtful that we will have a viable model with more than four predictors), we will be sensitive to an overall effect size of  $f^2 = 0.063$ . Although sensitivity is provided, we consider the analyses used in the evaluation of this pilot data to be focused on estimation of effect sizes for future studies rather than for inferential interpretation. Because of this, p-values (and criterion alpha levels) will not be corrected for multiple independent testing. We will also run an exploratory regression model with mean training hours per week.

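### Aim 2 asks a mediation question, but the plan states only VO2max–cognition correlations framed on the AE group, with no AE-versus-CONT estimate for VO2max

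*Combined protocol and SAP*

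**What the plan says.** The opening Specific Aims and the Statistical analysis plan (Specific Aim 2) both ask whether gains in estimated VO2max mediate cognitive improvement. The opening section predicts that VO2max "improvement in the AE group will predict cognitive gain with training at 12 weeks and 8 weeks" after training ends.

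Under Statistical analysis plan, Specific Aim 2:
- **Method.** VO2max "as a potential mediator will be evaluated using partial correlation coefficients from the regression model". No treatment-arm term is named.
- **Moderators.** The paragraph covers VO2max "as well as potential moderator effects of age, sex, and anticholinergic load to better formulate covariates in future models". Arm is not on that list.
- **Sensitivity.** "With a total sample size of 20 participants in the treatment group", the plan claims to detect r = 0.428 "at an alpha level of 0.05 with a power of 0.80". A second figure, f² = 0.063, follows for the overall effect "In a multiple regression with four predictor variables".
- **Status.** The plan describes these analyses as a source of effect sizes for later studies, not as a basis for inference, and leaves p-values uncorrected.

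The between-arm analyses are written elsewhere. Under Specific Aim 1: "Two-sample t-tests using the change in cognitive tests and functional scales as dependent variables will compare AE to CONT participants". Aim 1 adds an ANCOVA of change scores for its MCCB hypothesis, and Aim 3 has the same for UPSA. VO2max is not named in any of them. It is, however, a declared secondary outcome: "To confirm the cardiovascular effects in the AE group we will perform an exercise test on all participants". The schedule table places it at baseline, Day 84 and the 20-week follow-up.

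**The concern.** Mediation of a treatment effect has two links. Assignment to AE must raise fitness more than assignment to CONT does, and that extra fitness must carry the cognitive difference between arms. A correlation between two change scores speaks only to the second link, and does so observationally. Motivation, symptom change or medication change could move both scores together in either arm.

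Randomisation can answer the first link, and the data to do so will be collected, but no analysis of it is written. The pilot's stated purpose is to supply effect sizes for a larger study. A VO2max–MCCB correlation could reach that study labelled as mediation even if AE raised fitness no more than stretching did.

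**Working it through.** **1. Which participants does the sensitivity figure describe?** Inputs: alpha 0.05, power 0.80, r = 0.428 (Specific Aim 2). Sidedness is not stated; two-sided is assumed. By Fisher z, the detectable r = tanh[(1.960 + 0.842)/√(n − 3)].
- n = 20: 2.802/√17 = 0.680, so r = 0.591 (exact bivariate-normal calculation 0.579).
- n = 40: 2.802/√37 = 0.461, so r = 0.431 (exact 0.426).
- Solving for n at r = 0.428: (2.802/0.457)² + 3 ≈ 40.5.
- Power at r = 0.428 with n = 20: Φ(0.457 × √17 − 1.960) = 0.47 (exact 0.49).

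A one-sided test at n = 20 gives 0.50 to 0.54, so sidedness does not explain the figure. The text says 20 and the number fits both arms together. The companion f² = 0.063 fits neither size: the overall four-predictor test at 80% power needs f² of about 0.82 at n = 20 or 0.34 at N = 40.

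**2. Is the first link analysed anywhere?**

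| Analysis in the plan | Outcome | AE versus CONT? |
|---|---|---|
| Aim 1 t-tests and ANCOVA | cognitive tests, functional scales | yes |
| Aim 2 correlations and regression | cognitive improvement, with VO2max as predictor | no arm term stated |
| Aim 3 ANCOVA | UPSA | yes |

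No row has VO2max as the outcome.

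**3. What can the correlation show when the first link is absent?** Simulation with 20 per arm, 5,000 to 8,000 trials per setting, normal change scores, equal mean VO2max change in both arms, and the same assumed shared-cause correlation in each arm. The table gives how often the AE-only Pearson correlation is positive with p<0.05, beside the approximation Φ(atanh(r) × √17 − 1.960).

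| Assumed r | Simulated | Approximation |
|---|---|---|
| 0.3 | 25–26% | 25% |
| 0.4 | 42–43% | 42% |
| 0.5 | 64% | 62% |
| 0.6 | 83–84% | 82% |

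At r = 0.54, the within-group value reported under Preliminary Studies, it is 73%. Pooling all 40 without an arm term does not help: the pooled correlation is positive and significant in 47% to 99% of trials over r = 0.3 to 0.6. These runs use a plain correlation, not the partial one. Adjusting for age, sex and anticholinergic load would not remove a shared cause such as motivation.

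**4. What does bringing in the control arm achieve?** Consider requiring both a significant AE-versus-CONT difference in VO2max change and a significant arm-adjusted slope.
- *AE has no effect on VO2max:* both are met in 1% to 3% of trials. The first test alone caps the rate near 2.5%, apart from simulation error.
- *AE raises VO2max, with the same shared cause and no causal path to MCCB:* at d = 0.8 both are met in 31%, 50%, 64% and 69% of trials for r = 0.3, 0.4, 0.5 and 0.6; at d = 1.0, in 40% to 86%. As a check, power of the arm test times approximate power of the slope at N = 40 gives 0.69 × 0.47 = 0.32 and 0.69 × 0.99 = 0.68 at d = 0.8, and 0.87 × 0.47 = 0.41 and 0.87 × 0.99 = 0.86 at d = 1.0.

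**5. How precise is the VO2max contrast?** With 20 per arm, two-sided 0.05, power is 0.34 at d = 0.5 and 0.69 at d = 0.8; 80% power needs d of about 0.91. The 95% CI half-width is about 2.02 × √(2/20) = 0.64 SD.

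**The case against.** Four points on the other side deserve weight.

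- **The AE-only analysis set is inferred.** A reader might conclude that the plan confines Aim 2 to the AE arm. The sentence giving the method names no analysis set. The reference to the treatment group sits in the sensitivity sentence, whose figure fits 40. What stands is that the analysis set is inconsistent and the arm term unspecified.
- **The plan disclaims inference.** A reader might take 25% to 84% as the rate of false mediation claims this trial would make. The plan adopts no p<0.05 rule for Aim 2 and speaks only of a potential mediator. The percentages show how readily a correlation appears without mediation; they are not an error rate of the plan. The disclaimer lowers the stakes, but it does not turn a correlation into an estimate of mediation.
- **The control arm is not ignored.** VO2max is a secondary outcome measured in everyone, and the team's earlier study in older adults reported an AE-versus-control difference (p = 0.02) before its within-group correlation. The gap is an unwritten analysis, not missing data.
- **The remedy has limits.** A reader might infer that using both arms cuts false mediation findings to 1% to 3% in general. Step 4 shows that this holds only if AE leaves fitness unchanged. The protocol expects AE to raise fitness, and then adjusting for arm does not remove the shared cause. A significance gate on the VO2max contrast would also often suppress a true signal at this sample size.

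**Conclusion.** The concern holds in a limited form. Aim 2 poses a mediation question, and the stated methods cannot estimate its first link. No AE-versus-CONT analysis of VO2max, no arm term and no indirect effect is written, under either reading of the analysis set. The stated n = 20 and r = 0.428 contradict each other and must be reconciled.

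The consequence is a possibly misleading effect size passed to the follow-on study, not a formal false-positive claim. Its size depends on an assumed shared-cause correlation of 0.3 to 0.6 and no arm effect on VO2max. The value 0.54 under Preliminary Studies comes from a study in which AE did raise fitness, so it is not evidence of confounding alone. The change is worth making because the data will already be in hand.

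**What to change.** Amend the text of Specific Aim 2 as follows.
1. State that both arms are used, and recompute the sensitivity figures (r and f²) for the N actually analysed.
2. Estimate the AE-minus-CONT difference in VO2max change by ANCOVA with baseline VO2max, with a 95% CI.
3. Regress MCCB change on VO2max change with arm and baseline MCCB in the model.
4. Report the indirect effect with a bootstrap interval, labelled exploratory in line with the plan's non-inferential status.
5. Show the VO2max–MCCB correlation within AE and within CONT side by side.
6. Describe the result as an association where the estimated VO2max difference and its interval do not support the first link. Do not use a p<0.05 gate.
7. State two limits: the VO2max contrast is imprecise at 20 per arm, and the fitness–cognition link stays open to shared causes after adjusting for arm.

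The cost is SAP wording and a few lines of analysis code, with no new data, visits or participants. The word mediation becomes harder to earn, and the indirect effect from 40 people will have a wide interval.

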## **RESEARCH DESIGN AND METHODS**

**Study Design:** The study will be a randomized parallel group clinical trial to compare twelve weeks of AE with a control condition (stretching and balance training) in 40 participants with SCZ (20 per group).

**Description of study population:** Participants for the study will be 40 participants treated at our Atlanta VA with a diagnosis of SCZ. Diagnosis will be confirmed by chart review and by a structured diagnostic interview (Structured Clinical Interview for DSM-IV, SCID-Axis I, patient version). Inclusion/exclusion criteria will be evaluated by means of chart review and participant interview.

**Inclusion criteria:** (1) Diagnosis of SCZ; (2) male or female, ages 18-70; (3) maintained on stable doses of outpatient psychiatric medications for at least 30 days; (4) compliant with outpatient follow-up (defined as coming for at least 75% of outpatient appointments within the previous 12 months); (5) have a stable place to live; (6) access to transportation to the VA. Participants will be sedentary as defined by reporting <20 min/week of performing regular physical activity in the past month.

**Exclusion criteria:** (1) Bipolar disorder;

- Criteria to rule out participants unlikely to be able to comply with treatment schedule: (2) active substance dependence within the prior 30 days; (3) more than 2 psychiatric admissions within the prior six months
- Criteria to rule out participants unlikely to be able to benefit from treatment: (4) known HIV infection or AIDS; (5) history of traumatic brain injury; (6) seizure disorder; (7) known Alzheimer's disease or other dementia; (8) clinical history of mild cognitive impairment (MCI); (9) Parkinson's disease; (10) other current clinically significant neurological disease, (11) unstable medical condition that would be expected to interfere with fitness training; (11) significant hearing or visual impairment.

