**Specific Aim 3:** Compare changes in performance-based measurement of functional abilities (by the UPSA) in the AE vs. CONT training groups. We predict that the AE group will have greater improvement in the UPSA than the CONT group at the end of treatment and at three months follow up.

**Statistical analysis:** The statistical approach for Spec Aim 3 will be similar to that of Spec Aim 1. Descriptive statistics will be generated with 95% confidence that our sample-based estimates will be within 0.20 SD of the population values. Hypotheses will be tested (and effect size estimates will be generated) with a univariate ANCOVA looking at change scores with baseline measures plus age, sex, and anticholinergic load as covariates. With a total sample size of 20 participants per group we will be sensitive to an effect size in UPSA scores of  $f=0.481$  (alpha=0.05: power=0.80). This power and effect size will enable us to detect changes in UPSA scores of about 14%, a clinically meaningful change. A similar analysis (with identical sensitivity) will be used to assess the stability of the treatment effect through a univariate ANCOVA of change scores between the post-treatment and 3 month follow up measurements with post-treatment scores used as the covariate.

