## Sample size determination

Sample size calculations for our primary outcome measure (MCCB) are based on several studies of AE compared to a control condition in which the effect sizes average approximately 0.5 (Dustman et al. 1984; Fabre et al. 2002; Heyn et al 2004; Hotting et al. 2012; Chapman et al. 2013). We also based estimated power on studies of cognitive remediation in SCZ, including a meta-analysis (Wykes et al. 2011) and studies of Posit Science computerized remediation (Fisher et al. 2010). The average effect size of the above studies is 0.5. With alpha set at 0.05, an effect size of 0.5 will yield a power of 0.80 for our **planned sample size of 20 completers per treatment group (with dropouts replaced)**. This sample size will be adequate to detect significant between group differences in MCCB change scores. More importantly for a pilot study, this sample size will allow us to estimate effect sizes specific to the target Veteran population with sufficient confidence to be useful in determining the sample size required for a future full Merit Review proposal (if indicated by the results of this pilot study). Participant retention will be an important issue. We estimate liberally from our prior work (cognitive remediation study) that *dropouts will be approximately 25%, so we will need to recruit 53 subjects in order to obtain the 40 completers needed for analysis.*

**Roles of members of the research team.** Please see delineation of roles in Budget Justification.

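### The Aim 3 claim of 95% confidence of being within 0.20 SD is not met for a mean: the half-width is 0.47 SD with 20 per group, 0.32 SD with 40 and 0.28 SD with all 53 recruits

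*Combined protocol and SAP*

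**What the plan says.** In the Statistical analysis plan, the paragraph on Specific Aim 3 (UPSA) makes a numerical claim about precision: "Descriptive statistics will be generated with 95% confidence that our sample-based estimates will be within 0.20 SD of the population values". It gives no sample size, SD or correlation for that figure. Later in the same paragraph, the power statement uses 20 per arm: "With a total sample size of 20 participants per group we will be sensitive to an effect size in UPSA scores of" f = 0.481.

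The section Sample size determination expects 25% dropout, "so we will need to recruit 53 subjects in order to obtain the 40 completers needed for analysis". It also says why the sample matters for a pilot: "this sample size will allow us to estimate effect sizes specific to the target Veteran population with sufficient confidence" to help size a later, full trial.

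**The concern.** A 95% margin of 0.20 SD is tight for a study with 20 people per arm. At n = 20 the standard error of a mean is already 1/√20 = 0.22 SD, larger than the margin claimed at 95% confidence.

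What is at stake is how readers understand the precision of the Aim 3 estimates. Estimation for a future trial is a declared purpose of this sample, and this is the only sentence in the analysis plan that puts a number on the precision of an estimate; the other figures concern power and detectable effects. A reader who trusts it would think the UPSA descriptive results much firmer than they can be.

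**Working it through.** **Inputs**
- Stated precision: 0.20 SD at 95% confidence (Statistical analysis plan, Specific Aim 3), read as two-sided.
- n = 20 per arm (Specific Aim 3; Study Design; Sample size determination).
- N = 40 completers in total (Study Design; Sample size determination).
- N = 53 recruited (Sample size determination; 40/0.75 = 53.3). Since 40 completers are to be analysed, 53 is a best case that only baseline summaries could use.

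**Attempt to reproduce 0.20 SD.** In units of the SD of the variable summarised, the 95% half-width of a mean is t(0.975, n−1)/√n.

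| n | Calculation | Half-width (SD) | Ratio to 0.20 |
|---|---|---|---|
| 20 | 2.093/√20 | 0.468 | 2.34 |
| 40 | 2.023/√40 | 0.320 | 1.60 |
| 53 | 2.007/√53 | 0.276 | 1.38 |

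The stated figure is not reproduced at any of the three sizes.

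**Confidence actually attached to 0.20 SD.** With T the t distribution function on n−1 degrees of freedom, this is 2·T(0.20√n) − 1:
- n = 20: 0.618
- n = 40: 0.787
- n = 53: 0.849

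**More favourable conventions**
- SD treated as known, 1.96/√n: 0.438, 0.310 and 0.269 SD at n = 20, 40 and 53. The confidence of being within 0.20 SD is then 0.629, 0.794 and 0.855.
- One-sided 95%, t(0.95, n−1)/√n: 0.387, 0.266 and 0.230 SD.

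Neither reaches 0.20 SD, even with 53.

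**Sample needed for one mean at 0.20 SD**
- SD known: (1.96/0.20)² = 96.04, so 97.
- t-based: the smallest n is 99, where the half-width is 0.1994 SD.

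**Difference between arms, the contrast in Aim 3.** Before covariate adjustment, in SD units of the analysed variable, t(0.975, 38)·√(2/20) = 2.024 × 0.316 = 0.640 SD, which is 3.2 times the stated value.

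**Conditions under which 0.20 SD could hold**
- Mean change in raw-score SD units, equal variances at both visits, pre-post correlation r: the half-width is multiplied by √(2(1−r)). Pooling all 40, 0.320·√(2(1−r)) = 0.20 gives r = 0.80. Within an arm of 20, 0.468·√(2(1−r)) = 0.20 gives r = 0.91.
- Covariate-adjusted mean, half-width multiplied by √(1−R²): R² must be about 0.61 with 40, or 0.82 with 20.

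**The case against.** The strongest reply is that the sentence does not say it concerns a mean, nor which SD it uses. Aim 3 is about change, and the description of the UPSA under Secondary outcome measures calls its test-retest reliability excellent. A pooled mean change in raw-score SD units would meet 0.20 SD at a pre-post correlation of about 0.80. On that reading the fault is an unstated assumption, not a wrong sum.

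Part of this stands. The estimate is unnamed, and the conclusion must be limited to a mean in SD units of the variable summarised. But the plan gives no correlation, and calling reliability excellent supplies no number. The rescue also needs the two arms pooled, which is not the comparison Aim 3 makes; within one arm the correlation would have to be about 0.91. Baseline summaries are not rescued at all.

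The second reply is that nothing depends on the figure. The Aim 3 hypothesis is tested by ANCOVA with its own sensitivity statement, and the sample size rests on an assumed MCCB effect of 0.5. Nothing shows that a later trial would be sized from this sentence. That is correct, and it keeps the point minor.

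A third reply is that a margin in population SD units calls for the known-SD calculation. That gives 0.44, 0.31 and 0.27 SD and 97 participants, with the same conclusion.

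**Conclusion.** The concern holds: the sentence is wrong as written for any simple mean at the planned numbers. The 95% half-width is 0.47 SD per arm, 0.32 SD with 40 pooled and 0.28 SD with all 53 recruits, against the stated 0.20 SD. About 99 participants per mean would be needed (97 with the SD known).

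This rests on a two-sided 95% interval, independent participants, approximately normal means, and the SD of the variable being summarised. It does not rule out that 0.20 SD was meant for another estimate under a high correlation or R², but the documents state no such estimate or assumption. Severity is minor, because the error affects only the description of precision.

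**What to change.** Replace the sentence in Specific Aim 3 with wording such as: *With 20 per group, 95% confidence intervals will have half-widths of about 0.47 SD for each arm mean (0.32 SD pooling all 40) and about 0.64 SD for the between-arm difference before covariate adjustment, in SD units of the analysed variable. The pilot effect size will be reported with its 95% confidence interval.*

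If 0.20 SD was intended for a different estimate, the plan should name that estimate, the SD used as the unit and the correlation or R² assumed.

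The cost is one sentence of wording. Sample size, visits and analyses stay as they are.

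### The Aim 3 UPSA sensitivity of f=0.481 does not follow from its stated inputs, which give f=0.456 as in Aim 1; the error is conservative and minor.

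*Combined protocol and SAP*

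**What the plan says.** In the Statistical analysis plan, Specific Aim 3, the UPSA hypotheses are tested with a "univariate ANCOVA looking at change scores with baseline measures plus age, sex, and anticholinergic load as covariates". The sensitivity statement reads "With a total sample size of 20 participants per group we will be sensitive to an effect size in UPSA scores" of f=0.481, with "alpha=0.05: power=0.80". The text converts this to a detectable UPSA change of about 14% and calls that clinically meaningful. It gives no UPSA mean or SD. It then adds: "A similar analysis (with identical sensitivity) will be used to assess the stability of the treatment effect", using an ANCOVA of change from post-treatment to follow-up in which the post-treatment score is the only covariate named.

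Aim 3 is tied to Aim 1: "The statistical approach for Spec Aim 3 will be similar to that of Spec Aim 1". Specific Aim 1 describes an ANCOVA of change scores with the same four covariates and states "With a sample size of 20 completers per treatment group, we will be sensitive to a within-between interaction effect size" of f=0.456, again at alpha 0.05 and power 0.80.

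The Sample size determination section confirms the number to be analysed: "planned sample size of 20 completers per treatment group (with dropouts replaced". It plans to recruit 53 people to reach 40 completers.

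**The concern.** Two sensitivities are given for what reads as one design. The minimum detectable f for a two-group ANCOVA depends on the number analysed, the error degrees of freedom, alpha and power. It does not depend on the outcome's scale, so UPSA and MCCB should share one value unless some other input differs. The plan names no such input.

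The Aim 3 figure also supports two further statements: the detectable change of about 14%, and the sensitivity of the follow-up analysis. The Sample size determination section says the pilot is meant above all to supply effect sizes for planning a larger study. A detectable effect that its own design does not give should not be carried into that work unexplained.

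**Working it through.** **Inputs** (Statistical analysis plan, Aims 1 and 3; Sample size determination)
- 20 per group, so N = 40.
- Four covariates: baseline, age, sex, anticholinergic load.
- Error df = 40 − 2 − 4 = 34; numerator df = 1.
- Alpha = 0.05. Sidedness is not stated; the 1-df F test is two-sided.
- Power = 0.80.

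**Formula.** Power = P[F′(1, df, λ) > F(0.95; 1, df)], where F′ is the noncentral F and λ = f²N. Solve for f at power 0.80. For two equal groups, d = 2f.

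**Step 1: reproduce Aim 1.** N = 40 and df = 34 give f = 0.4560. This is Aim 1's stated 0.456 exactly, with d = 2 × 0.456 = 0.912.

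**Step 2: apply the same inputs to Aim 3.** They are identical, so f = 0.4560 again. At the stated f = 0.481 (d = 0.962), power is 0.840.

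**Step 3: can another reading at N = 40 give 0.481?**

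| Variant at N = 40 | Detectable f |
|---|---|
| 0 to 7 covariates | 0.4546 to 0.4573 |
| One-sided 0.05 (0 and 4 covariates) | 0.400 to 0.401 |
| Alpha 0.025 (0 and 4 covariates) | 0.504 to 0.506 |
| Power 0.85 (0 and 4 covariates) | 0.486 to 0.488 |
| Numerator df 2 (0 to 4 covariates) | 0.511 to 0.513 |
| Repeated measures, between or within-between | at most 0.455 |

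None gives 0.481. With λ = f²N, the value appears near N = 36: 0.4806, 0.4811 and 0.4826 with 0, 1 and 4 covariates.

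**Step 4: follow-up analysis.** With one covariate, df = 40 − 2 − 1 = 37 and f = 0.4549. The difference from the four-covariate model is 0.4560 − 0.4549 = 0.0011.

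**Step 5: size.** 0.481 / 0.456 = 1.055, so the detectable effect is overstated by about 5%. If the 14% is proportional to f, the corrected value is 14 × 0.456 / 0.481 = 13.3%.

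**The case against.** **The two figures may come from different routines.** Aim 1 labels its f a within-between interaction; Aim 3 speaks only of an effect size. Some software defines f from partial eta-squared, with λ = f² × error df. At N = 40 the λ needed is 40 × 0.4546² = 8.27 with no covariates, 40 × 0.4552² = 8.29 with two, and 40 × 0.4560² = 8.32 with four. Dividing by df 38, 36 and 34 and taking square roots gives f = 0.466, 0.480 and 0.495. So a value close to 0.481 can arise without changing N. But it needs two covariates where the plan names four, it is still not 0.481, and the plan does not state that convention. The objection shows that the origin of 0.481 is unknown. It does not rescue the figure.

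**The consequences are slight.** This stands. UPSA is a secondary outcome, the sample size was set on MCCB, and the study is a pilot.

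A reader might also infer four stronger things that the documents do not support:
- *That Aim 3 is underpowered.* The error runs the other way: the design detects a smaller effect than stated.
- *That the follow-up statement fails because its covariates differ.* The difference moves f by only 0.0011. The figure carried over is off solely because 0.481 is off.
- *That 18 per group was really assumed.* Aims 1 and 3 and the sample size section all give 20 per group, and dropouts are to be replaced. N = 36 is a numerical coincidence or a guess.
- *That the 14% is wrong.* Without a UPSA mean and SD it can be neither confirmed nor refuted, and 13.3% is close to the plan's own rounded wording.

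**Conclusion.** The point holds as a minor reporting error. From the stated inputs, Aim 3's sensitivity is f = 0.456, not 0.481. The design has power 0.84 at the stated effect, and the detectable effect is overstated by about 5% (d 0.96 against 0.91). This rests on a two-sided test, all 40 completers analysed, and the usual definition λ = f²N, which reproduces Aim 1's figure exactly. No test, sample size or planned analysis changes. The statement that the follow-up analysis has the same sensitivity is essentially true between the two models. For the 14%, the supportable criticism is that its basis is not given.

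**What to change.** In the Statistical analysis plan, Specific Aim 3:
1. Replace f=0.481 with f=0.456.
2. Leave the equal-sensitivity statement for the follow-up analysis as it is; it then refers to the corrected figure.
3. State the assumed UPSA mean and SD and recompute the detectable percentage change from f=0.456. Expect about 13.3% if the present figure was scaled from f.

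The figure should not be relabelled as 18 per group, because that would contradict the 20 per group stated elsewhere. The cost is a few words in the SAP; recruitment, data collection and analysis are unaffected.
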